The 40 subjects will be randomly assigned to either a control group or an intervention group.

Survey

A 23 item PedsQL 4.0 pre-survey will be administered to pediatric patients to establish a baseline at their wellness visits. The parent of the patient will also complete the PedsQL survey. The patients' BMI and blood pressure will be recorded. At the end of the 6 month period, the same PedsQL 4.0 will be administered again to both the patient and parent at the scheduled 6 month weight check that is standard of care.

We will use a text message application created by the Loyola informatics team. This application will be able to text the subjects using their cell phone number via an email service from the provider. For example, [name]. This allows the research team to send text messages through an application without using a personal phone number. In addition, it offers automatic responses that will save them when sending messages to the patient.

For six months, patients in the study will receive a text message twice per week.

Text messaging

There will be two groups within this study—a control group and an intervention group. For the control group, they will receive two text messages weekly. The first text message will ask if they completed the recommended activity. When they respond, they will receive a second text message stating, "Thanks for your response."

In the intervention group, the first text message will ask if they completed the recommended activity. If they respond yes, they will receive a positive reinforcement response comprising the words "Great job! We're so proud of you! Keep up the good work!". If they respond no, they will receive a text message stating "Thanks for your response".

Study Activities: See attached schedule for details

The weekly activities we will recommend for the subjects include:

1. Walking for 30 minutes 3 times a week
2. Speed walk for 30 minutes 3 times a week
3. Walk up and down stairs for 30 minutes 3 times a week
4. Jogging for 30 minutes 3 times a week
5. Jumping jacks for 30 minute 3 times a week

Data:

All patient data will be stored in a secure REDCap database located at hsddb.luhs.org/redcap.

Statistical analysis:

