In this study, patients who are age 18 and under with a BMI in at least the 95th percentile will be randomized to an intervention or control text-messaging cohort using a 1:1 random allocation. Subsequently, they will be asked to complete assigned exercises. For six months, these patients will receive a text message twice per week asking whether they completed their assigned exercises. For those in the intervention group, when they respond "Yes", they will receive a positive reinforcement response comprising the words "Great job! We're so proud of you! Keep up the good work!". Otherwise, when they respond "No", they will receive a message saying "Thanks for your response". For those assigned to the control group, they will always receive the message "Thanks for your response" regardless of whether they complete or do not complete the assigned exercises.

Six months following randomization, one goal of the proposed study is to test the null hypothesis that average total score on PEDSQ4.0 questionnaire between the two groups are equal. With a proposed sample size of 20 assigned to receive the positive reinforcement response and 20 assigned to receive the control response (N = 40), the study will have power of 80.0% to yield a statistically significant result. This computation assumes a mean difference between the two

cohorts of 14.8 points (corresponding to means of 81.8 for the positive reinforcement cohort and 67.0 for the control response cohort) and a common within-group standard deviation of 16.3 points⁷. This computation also assumes the criterion for significance (alpha) is 0.05 and that the test will be 2-tailed, meaning an effect in either direction will be interpreted.

Recommended Protocol Text for the Analysis Plan

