Patients under age 18 with a BMI in at least the 95th percentile will be asked to complete assigned exercises and will receive text messages asking them if they completed such exercises. At baseline and the end of the study, the participants will complete the 23-item PEDSQ4.0 assessment. For each participant, the baseline value will be subtracted from the 6-month value. An independent samples t-test will be used to compare this delta score between the cohort assigned to receive the positive reinforcement response and the cohort assigned to receive the control response. For this comparison, the normal distribution assumption of the delta score will be assessed using QQ plots and outliers will be assessed using box plots. The homogeneity of variances assumption will be assessed using Levene's test. If any parametric assumption is strongly violated, a non-parametric Wilcoxon rank-sum test may be used to compare ranked PEDSQ4.0 scores between the two cohorts. All analyses will be completed using SAS version 9.4 (Cary, NC) by a Biostatistician in the Clinical Research Office.

VII. Safety Monitoring Plan

There are no adverse events that could be associated with text messages we will send to the subjects. We will send these text messages on Monday early evening between the 5pm to 6pm. We chose this time because they will not be in school and are unlikely to be driving or doing activities that they could be distracted from when they receive the text, which could cause harm.

If there is an adverse effect, we will ask the subjects to notify the principal investigator of the project. We will review safety information once a month.

VIII. Literature Cited

References

- 1 Daniels et al. The role of the pediatrician in primary prevention of obesity. *Pediatrics*. 2015;136(1):e275
- 2 Snyder, et al. American academy of pediatrics. *Congenital Heart Disease*. 2012;7(2):200-201.
- 3 Health-Related Quality of Life (HRQOL) | CDC. (2018). Retrieved from <https://www.cdc.gov/hrqol/index.htm>
- 4 Eiser, et al. A review of measures of quality of life for children with chronic illness. *Archives of disease in childhood*. 2001;84(3):205-211.
- 5 Simon, et al. Assessment of children's health-related quality of life in the united states with a multidimensional index. *Pediatrics*. 2008;121(1):e118.
- 6 Swallen, et al. Overweight, obesity, and health-related quality of life among adolescents: The national longitudinal study of adolescent health. *Pediatrics*. 2005;115(2):340.

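### The safety plan does not address the exercise given to both arms, and adverse events are found only by participants' self-report, with no scheduled standard question

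*Combined protocol and SAP*

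**What the plan says.** Section VII (Safety Monitoring Plan) is short and is the only safety text. It opens with "There are no adverse events that could be associated with text messages we will send to the subjects". It then explains the hour at which texts are sent: participants are "unlikely to be driving or doing activities that they could be distracted from when they receive the text, which could cause harm". Events are to be found as follows: "If there is an adverse effect, we will ask the subjects to notify the principal investigator of the project". Review is monthly: "We will review safety information once a month". The section does not mention exercise and names no data source for the review.

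Section VI (Study Procedures) introduces its activity list with "The weekly activities we will recommend for the subjects include". The five entries are walking, speed walking, stairs, "Jogging for 30 minutes 3 times a week" and "Jumping jacks for 30 minute 3 times a week". All five have the same session length and weekly frequency. The statistical analysis text in Section VI uses a firmer word, saying of all randomised patients: "Subsequently, they will be asked to complete assigned exercises". The recommended analysis-plan text that follows also treats the exercises as assigned. Both arms receive the activities and are texted about completion for six months; they differ only in the reply to a yes.

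**The concern.** The physically active part of the protocol is absent from the risk assessment. The study supplies exercise to participants aged 13 to 18 with a BMI above the 95th percentile and follows its completion for half a year, yet the one hazard that Section VII discusses is distraction when a text arrives.

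The second gap is in how events are found. Participants are asked to report, but nobody is scheduled to ask them. A safety plan built around the messages gives an adolescent little cue that a sprain, or symptoms while jogging, is something the study wants to know about. If such events go unreported, the monthly review has nothing to work from, and the trial could end by stating that no adverse events occurred without having asked.

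**Working it through.** The plan gives no figure on this point. Its one computed figure, 80.0% power for the PedsQL comparison, reproduces (79.9% by the noncentral t calculation with 20 per arm, difference 14.8, SD 16.3, two-sided alpha 0.05), but nothing below depends on it. The check is mainly one of reading, with an illustration of scale.

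**Step 1: set the sections side by side.**

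| Element | Where | What is stated |
|---|---|---|
| Exposure assessed for risk | Section VII | Text messages only |
| Exposures given to participants | Section VI and analysis-plan text | Text messages and exercise, both arms, six months |
| How events are found | Section VII | Participant notifies the principal investigator |
| Content of the texts | Section VI, Text messaging | Completion of the activity only |
| Content of the six-month visit | Section VI, Survey | Repeat PedsQL for patient and parent, at the routine weight check |
| Interim contact | Section VI | Routine weight checks that may fall at one, three or six months; no event collection described |
| Entry check | Section IV | The attending confirms suitability; no exercise criterion given |
| Exclusions | Section VI | Developmental delay with inability to read; no cell phone |
| Monthly review | Section VII | Frequency given, data source not named |

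No row contains a question about adverse events put to the participant or parent, and no row assesses exercise risk.

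**Step 2: scale of the unassessed exposure.** Assume one listed activity per week, done in full, for 26 weeks.

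- Per participant: 3 × 26 = 78 sessions; 78 × 30 min = 2,340 min = 39 hours.
- Over 40 participants: 78 × 40 = 3,120 sessions; 39 × 40 = 1,560 hours.

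This is an illustration, not a maximum. Adherence may be lower. The weekly load may also differ, because the activity schedule that Section VI calls attached is not in the text available.

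**Step 3: what reliance on self-report could cost.** The documents give neither an event risk nor a reporting proportion, so both are assumed. With per-participant risk r and reporting probability s, independent across 40 participants, the chance of recording at least one event is 1 − (1 − r·s)^40.

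| Assumed risk r | s = 100% | s = 50% | s = 25% |
|---|---|---|---|
| 5% | 1 − 0.95^40 = 87% | 1 − 0.975^40 = 64% | 1 − 0.9875^40 = 40% |
| 10% | 1 − 0.90^40 = 98.5% | 1 − 0.95^40 = 87% | 1 − 0.975^40 = 64% |

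The fall across each row is the part attributable to incomplete reporting. A prompted question acts on s and on nothing else.

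**The case against.** Much can be said for the plan. The opening sentence of Section VII is limited to text messages, and the request to notify the principal investigator is not. An exercise injury can be reported by that route and can reach the monthly review. Participants are told to report, so this is instructed self-report. The activities are ordinary ones, called recommendations in Sections I and VI. The attending confirms each candidate's suitability, and routine weight checks bring some participants back before six months. The consent pages are not in the text available, so what families are told about exercise there cannot be assessed.

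These points stand and narrow the concern, but they do not remove it. Neither the attending's confirmation nor the weight checks are described as screening for exercise risk or as collecting events. Whether recommended or assigned, the activities are supplied by the study and followed for six months.

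Four stronger readings are tempting and are not supported:

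- *That the protocol declares adverse events impossible.* It says so only of the text messages, and it then provides for adverse effects in general.
- *That exercise events cannot reach the review.* They can, by self-report; what is missing is a scheduled, uniform question.
- *That events will be recorded unevenly between arms.* Praise might raise completion in the intervention arm, but the documents do not show that it will. The reporting instruction does not differ by arm.
- *That the small sample measures the flaw.* Zero events in 40 gives a one-sided 95% upper bound of 1 − 0.05^(1/40) = 7.2%. That bound follows from the sample size alone and would be the same under a perfect safety plan.

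**Conclusion.** The concern holds as an omission in risk assessment and in active collection. Section VII does not cover the exercise component, and self-report to the principal investigator is the only stated way in which events are found. Exercise-related events may be under-recorded, and a report of no adverse events would be weakly supported.

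The size is not known. The 39 hours per participant rests on one listed activity per week, full adherence and 26 weeks. The capture probabilities rest on assumed risks of 5% and 10% and assumed reporting of 25% to 100%. The comparison of PedsQL change scores does not depend on this point. Because both arms exercise, the randomised comparison would not isolate harms of exercise in any case; the gain is in the completeness of the safety record. The change should be made because it is cheap and uses visits that already occur.

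**What to change.** 1. Reconcile Section VII with the activity list in Section VI, so that the risk assessment covers every activity the study gives to participants. Settle whether the exercises are recommended or assigned, and use one term throughout.
2. State that reportable events include injury or symptoms during the study activities, as well as anything related to the messages.
3. Ask one fixed question about such events, worded identically in both arms and with a stated recall period, at the six-month visit and at any interim routine weight check that takes place. Keep the existing request to notify the principal investigator.
4. Record each answer in REDCap. Interim answers feed the monthly review; six-month answers feed the final safety report. A question asked only at six months would come too late to inform monthly review during that participant's exposure, which is why the interim checks matter.

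The cost is one question, one REDCap field and revised wording in Section VII. There will be some recall error, and the recorded event count will probably rise because someone is asking. Not every participant will have an interim check, so some will be asked only once. How any event is managed clinically is left to the sponsor.
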